6.4.2 Secondary Analyses of Primary Outcomes

The secondary analysis of the primary outcome will take place on a subset of participants defined by the per-protocol population with individuals being censored at the earliest of end of their trial treatment (4 weeks after last dose) or last follow-up. The analysis will otherwise match the approach described above for the primary analysis.

6.4.3 Sensitivity Analyses

No sensitivity analyses of the Primary Outcome have been planned according to the protocol.

6.5 Secondary Outcome Analyses

6.5.1 Primary Analysis of Secondary Outcomes

All secondary outcome (except for AEs and SAEs) will be analysed on the modified intention to treat population. The secondary outcomes of adverse and serious adverse event counts will be analysed on the safety population.

All time to event secondary outcomes will be analysed the same way as the primary outcome.

All count secondary outcomes, number of hospital readmissions and number of moderate exacerbations, will be analysed using a negative binomial regression model. If there is no evidence of over-dispersion, a Poisson regression model will be used in place.

All continuous longitudinal outcomes (repeated measurements) will be compared using mixed effects model with patient as a random effect to account for repeated measures over time. This method will enable handling of missing data within the follow-up visits.

This trial has a single primary outcome, therefore there will not be a formal adjustment for multiple significance testing.

6.5.1.1 Time to event analyses

Will utilise the same methodology and presentation as the primary time to event outcome

6.5.1.2 Continuous Longitudinal Outcomes

All continuous longitudinal outcomes (repeated measurements) will be compared using mixed effects model with explanatory variables of treatment arm, stratification variables, visit number in weeks (categorical) and baseline value as fixed effects with participant identification as a random effect to account for repeated measures over time. This method will be able to handle missing data during the follow-up measurements. Adjusted mean differences alongside two sided 95% CI and P-value will be reported for these outcomes. Mean and standard deviation at baseline and over 48 weeks of the observed data will be presented by treatment arm. The adjusted mean change from baseline in each arm (with 95% confidence intervals) and the adjusted mean difference between groups (with 95% confidence intervals) will be presented alongside the 2-sided p-value from the model.

The model residuals corresponding to the continuous longitudinal outcomes will be assessed for normality by performing the Shapiro-Wilk Test.

Data will be assessed for the normality assumption using visualisation, taking into account sample size for each variable, the nature of potential outliers, and similarity between mean and median values (recognising formal statistics to test for normality

often lead to spurious results). If the distribution of the variable is found to be far from normally distributed, a log transformation will be used to modify the non-normality. In these cases adjusted geometric mean on the original scale (i.e. after anti-logging the result on the log scale) alongside standard errors on the log scale will be presented of the observed data. Geometric mean ratios from the model (with associated 95% CI and 2-sided p-value) will be reported to compare treatment groups.

Should a log transformation not correct for non-normally distributed data a non-parametric test such as the Mann Whitney U test can be utilised to assess the distribution of ranks between the treatment arms. Adjustment for other variables in the model including baseline value will not be possible and the Median (inter-quartile range), minimum, maximum of the observed data in each treatment arm will be presented along side the 2-sided p-value.

Further analysis of the participant reported outcomes will be carried out assessing the treatment effect by visit. Mean and standard deviation (SD) in each treatment arm will be calculated at baseline and each follow-up time point for each outcome using the observed data.

A mixed effect model with dependent variable of the outcome at baseline and follow-up time points; explanatory variables of treatment arm, stratification variables, visit number in weeks (categorical), baseline value, and an interaction term between treatment and visit as fixed effects with participant identification as a random effect to account for repeated measures over time will be fitted for each outcome. Adjusted mean change from baseline in each treatment arm as well as adjusted mean difference between treatment arms at each time point with 95% confidence intervals and p-value will be reported.

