4 TRIAL DESIGN

This will be a single-centre, double-blinded, randomised, placebo-controlled trial comparing mepolizumab 100mg versus placebo in patients with eosinophilic COPD, started following their index admission to hospital. 238 participants will be recruited over a 3-year period.

Once eligibility criteria are met and written informed consent is obtained at the initial visit, patients will be randomised into a 48-week treatment period in which they will receive monthly subcutaneous injections of either 100 mg mepolizumab or a matching placebo. Secondary outcomes will be measured at baseline (week 0), 4 weeks, 8 weeks, 12 weeks, 24 weeks, 36 weeks and 48 weeks. Treatment groups will remain blinded until the analysis is complete.

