4.6 Other Analysis Populations

N/A.

5 General Issues for Statistical Analysis

Continuous Outcome data with symmetric distribution will be described with summary statistics such as the mean and standard deviation (SD). Skewed continuous Outcome data will be described using the median and interquartile range (IQR). Determination of symmetry will be made informally by visualisation, taking into account sample size for each variable, the nature of potential outliers, and similarity between mean and median values (recognising formal statistics to test for normality often lead to spurious results).

Categorical Outcome data will be summarised with numbers (absolute frequency) and percentages.

Summary tables for both continuous and categorical outcome data will be presented by treatment group and overall in the intention to treat population.

For continuous outcomes that follow a normal distribution, we will compute the adjusted mean change from baseline for each treatment arm, presenting it alongside the corresponding 95% confidence interval.

For non-normally distributed continuous outcomes, and if transformations prove ineffective in enhancing normality, we will resort to a non-parametric approach—specifically, the Wilcoxon rank-sum test (Mann-Whitney two-sample statistic) to compare outcome values between the two treatment arms at each time point without applying baseline adjustments. The calculated statistics will include the median, interquartile range, as well as the minimum and maximum values for each treatment arm.

All time to event analyses will be accompanied by Kaplan-Meier survival curves to compare the survival rate between the two groups.

To visually represent non-normally distributed outcomes, we will create a whisker plot, illustrating the median along with the 25th and 75th percentiles, minimum, and maximum values for each treatment arm.

For visual representation of all other normally distributed continuous outcomes, line plots will be produced for the adjusted mean change from baseline in each treatment arm alongside a 95% confidence interval using time since randomisation on x-axis and adjusted mean change from baseline at y-axis.

5.1 *Derived/ Computed Variables*

Treatment allocation received

The reason for Protocol deviation concerning participants who received incorrect trial drug/placebo and the treatment allocation variables will be used to derive a binary

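### SPPB, handgrip and parametrically analysed eosinophils have no planned visit-specific estimate, and line plots drawn from their only adjusted model would be parallel by construction

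*SAP*

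**What the plan says.** SAP 6.5.1.2 specifies one main model for all continuous longitudinal outcomes. Its fixed effects are "explanatory variables of treatment arm, stratification variables, visit number in weeks (categorical) and baseline value as fixed effects", fitted "with participant identification as a random effect to account for repeated measures over time". The result is a single contrast per outcome: "Adjusted mean differences alongside two sided 95% CI and P-value will be reported for these outcomes".

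The same section then adds a model with a treatment-by-visit interaction, introduced by: "Further analysis of the participant reported outcomes will be carried out assessing the treatment effect by visit". SPPB and handgrip are performance measures and the eosinophil counts are laboratory measures, so on a plain reading they fall outside it.

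SAP section 5 asks, for normally distributed continuous outcomes, that "line plots will be produced for the adjusted mean change from baseline in each treatment arm alongside a 95% confidence interval". The horizontal axis of these plots is to be follow-up time. The section does not name the model that supplies the plotted values. For outcomes that stay non-normal after transformation, section 5 plans rank tests and whisker plots instead, with a comparison at each time point.

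The visit schedule is in Protocol section 4: "Secondary outcomes will be measured at baseline (week 0), 4 weeks, 8 weeks, 12 weeks, 24 weeks, 36 weeks and 48 weeks". Participants randomised from July to December 2023 have planned follow-up of 44 down to 24 weeks (Protocol 4.1, SAP 2.1).

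**The concern.** A model with treatment and visit main effects but no interaction assumes the same treatment difference at week 4 as at week 48. Neither document argues for that. Baseline is taken around an acute admission (Protocol 7.6), so the first visits fall in recovery, and a difference that builds up or fades is plausible.

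Two things are at stake for SPPB, handgrip and parametrically analysed eosinophils. First, a published time-course plot could show a constant gap that the model imposed, and a reader could take it for a finding. Second, the one reported difference is a weighted average over visits whose weights depend on who is still being measured, so the quantity estimated is not fixed in advance. Frailty is a named secondary objective, and SPPB and handgrip are its only measures.

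**Working it through.** The documents give no SD, within-person correlation, attrition rate or target difference for these outcomes, so there is no figure of the plan's own to reproduce. Everything numerical below except the visit schedule rests on stated assumptions.

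**1. Parallel lines.** Write the main model as y(i,j) = μ + τ·T(i) + visit(j) + β·baseline(i) + strata + u(i) + e(i,j). The adjusted gap between arms at visit j is [μ + τ + visit(j)] − [μ + visit(j)] = τ, the same for every j. The baseline and strata terms cancel because both arms are evaluated at the same values.

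A fit to one simulated data set shows this (238 participants, true difference = week/48, no missing data):

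| Week | 4 | 8 | 12 | 24 | 36 | 48 |
|---|---|---|---|---|---|---|
| Main-effects model | 0.69 | 0.69 | 0.69 | 0.69 | 0.69 | 0.69 |
| With treatment × visit | 0.31 | 0.33 | 0.56 | 0.74 | 0.98 | 1.24 |

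The second row averages (0.31 + 0.33 + 0.56 + 0.74 + 0.98 + 1.24)/6 = 0.69. With complete data the main-effects coefficient is the equal average of the visit differences, and the time course is lost.

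**2. Weights in the single coefficient.** Under a random intercept, the generalised least squares coefficient is Σ w(j)·δ(j), where δ(j) is the true difference at visit j and the weights sum to 1. Truncated participants' off-schedule final visits were left out.

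| Scenario | Weeks 4–12 | Week 48 |
|---|---|---|
| Complete data | 50% | 16.7% |
| 1/6 truncated (6 of 36 recruitment months, uniform), no other loss | 53% | 14% |
| Assumed 20% truncated, 25% attrition by week 48, correlation 0.6 | 60% | 10.5% |
| Assumed 35% truncated, 35% attrition, correlation 0.6 | 64% | 7.6% |

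**3. Effect on the estimate.** Take an outcome with SD 18 and 238 participants. At 20%/25% the weights for weeks 4, 8, 12, 24, 36 and 48 are 0.213, 0.197, 0.187, 0.166, 0.131 and 0.105.

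- (a) The effect builds linearly to −6 at week 24 and then holds, so the visit effects are −1, −2, −3, −6, −6, −6.
  - Equal average: −24/6 = −4.0.
  - SAP model: −(0.213 + 2×0.197 + 3×0.187) − 6×(0.166 + 0.131 + 0.105) = −1.17 − 2.41 = −3.58.
- (b) The effect is −6 to week 12 and then zero.
  - Equal average: −18/6 = −3.0.
  - SAP model: −6×0.597 = −3.58.

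With SE 1.955, the shifts are 0.42/1.955 = 0.21 SE in (a) and 0.58/1.955 = 0.30 SE in (b). The SAP model returns −3.58 for two opposite time courses.

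At 35%/35%, (a) gives −3.38 and (b) gives −6×0.644 = −3.86. With SE 1.980 the shifts are 0.62/1.980 = 0.31 SE and 0.86/1.980 = 0.43 SE.

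With one sixth truncated and no other loss, the estimates are −3.89 and −3.17, shifts of 0.11 and 0.17, less than a tenth of an SE.

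**4. Cost of the interaction.** The SE of the equal-weight average is 1.962 against 1.955 (+0.4%) at 20%/25%, and 2.000 against 1.980 (+1.0%) at 35%/35%.

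**The case against.** A prespecified average over follow-up is a legitimate summary, and Protocol 10.3.3 asks only for a mixed model with a patient random effect. Several limits on the point stand.

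- **Plots.** Section 5 names no model for them, and the by-visit paragraph in 6.5.1.2 says its model is fitted for each outcome. A reader might infer that the plots are certain to be parallel. The documents support that only if the plots come from the main model. It is the natural source, because it is the only adjusted model clearly planned for SPPB, handgrip and eosinophils.
- **Scope.** A reader might infer that no longitudinal outcome has visit-specific results. SGRQ, CAT, WEMWBS and LCADL already have them. Eosinophils that resist transformation get tests at each time point and no line plot. If a log transformation works, the constant gap is a constant ratio. Vital signs are safety data, which Protocol 10.3 summarises descriptively.
- **Early weighting.** A reader might infer that the missing interaction is what makes early visits dominate. The schedule alone gives weeks 4 to 12 half the weight, because three of the six follow-up visits fall there. An equal-weight average keeps that half: in (b) it is −3.0, although nothing remains at week 48.
- **Illustration.** The attrition and 20% to 35% truncation figures are assumptions, and SD 18 cannot apply to SPPB, which runs from 0 to 12. Shifts expressed in SE units carry over only if the effect has the same ratio to the SD. Adding the off-schedule final visits brings the 20%/25% estimates slightly closer to the equal average: −3.64 in (a) and −3.50 in (b).

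None of this supplies a visit-specific estimate for SPPB, handgrip or parametrically analysed eosinophils.

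**Conclusion.** The point holds in a limited form. SPPB, handgrip and parametrically analysed eosinophils have only an additive adjusted model. They have no planned visit-specific difference, and line plots drawn from that model cannot show whether an effect builds up or fades. This follows from the model's form and needs no numerical assumption beyond the source of the plots.

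The drift in weighting is secondary. It is small from truncation alone and about 0.2 to 0.3 SE at the assumed 20% truncation and 25% attrition, rising with heavier loss. It rests on a random intercept, a correlation of 0.6, loss equal in both arms and the two effect shapes chosen. It does not support a claim that the headline differences are invalid or seriously distorted.

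These are secondary outcomes. The time-to-event primary analysis is untouched, and the participant-reported outcomes already have by-visit estimates.

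**What to change.** Amend SAP 6.5.1.2 and section 5 before database lock:

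1. For SPPB, handgrip and parametrically analysed eosinophils, as well as the participant-reported outcomes, fit treatment, visit, treatment × visit, baseline value and stratification factors, with a participant random effect. Use follow-up visits only as the response. The existing by-visit model should not be copied unchanged, because it lists baseline both as a response and as a covariate.
2. Report the visit-specific differences with 95% confidence intervals, and state that the section 5 line plots come from this model.
3. Define the overall difference as the equally weighted average of the six visit-specific differences. With complete data this is the quantity estimated now.
4. State how truncated participants' final visits enter the model. Planned final visits at weeks 28, 32, 40 and 44 match no scheduled assessment week, and the schedule table places the final follow-up in the week 48 column.

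This stops the weights drifting with missing data. It does not remove the early emphasis that the schedule creates, so the average should be read beside the visit-specific results.

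The cost is SAP wording, one model term, a standard error about 0.4% to 1% larger under the assumed losses, and more reported contrasts.

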7.7.5 Truncated follow-up

Patients consented from July 2023 will be followed-up on a truncated visit model, with at least 20 weeks of dosing. Where applicable, the Visit 13 Final Follow-up (no dosing) visit will occur 4 weeks ± 7 days from final dosing visit. It will follow the same schedule of assessments as listed in section 7.7.4. Patients will only complete the visits as per the schedule outlined above up until their final dosing visit.

**please note that due to COVID-19 infection risk protocols within the hospital, only spontaneous sputum samples are collected as part of the standard of care*

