13.5 Protocol compliance

The trial team will monitor and review protocol compliance, deviations from the protocol will be captured both within the source data and the LCTU CDMS. Mepolizumab/placebo accountability will be monitored throughout the trial period. Where deviations frequently reoccur, this may meet the criteria for a Serious Breach of GCP and will be reported in line with Section 13.7. The trial team will not be required to report protocol deviations in instances where a participant is unable to produce a sample. Protocol deviations are not required for trial assessments omitted during a pandemic.

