4.1.2 Minor deviations

Participants visit/assessment not performed as per protocol

4.2 *Intention-to-treat Population*

The primary analysis for each efficacy outcome will be by ‘intention to treat’ analysis; all the participants randomised into the trial (regardless of whether they received trial drug) will be analysed in their allocated group. Outcome data obtained from all participants will be included in the data analysis.

4.3 *Modified intention-to-treat population*

The modified intention-to-treat will be comprised all the participants randomised to the trial (regardless of whether they received trial drug), analysed in their allocated group, where data is available. Therefore, participants with missing outcome data will be excluded from the analysis (i.e complete case analysis). No imputation will be carried out for the missing data.

4.4 *Per-protocol Population*

The per protocol population will contain all participants randomised who do not reach any of the listed definitions for major protocol deviations. Individuals without a major deviation will be included in the per-protocol population whilst on trial treatment, this is considered to be 4 weeks after the last dose. If a participant dies before ending trial treatment, time is capped by death date.

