6.5.3 Sensitivity Analyses

The primary analyses for all none time event outcomes (i.e continuous, binary and count outcomes) will consider any missing data to be missing at random (MAR) and complete case analysis carried out. However, if comparison of patterns of missingness and descriptive differences between treatment arms indicate this assumption is not valid, additional sensitivity analyses may be carried out and methods of imputation will be included in detail in the statistical analysis plan.

To ensure the reliability of the analysis of key secondary outcome measures, we will conduct a sensitivity analysis under various scenarios. This will involve evaluating the secondary outcomes; number of readmissions, number of exacerbations, and SGRQ (assessed for three sub-domains and the total score), to thoroughly assess the robustness of our results.

Individuals will be considered to have had some missing data for the two count variables if they have less than 47 weeks (48 weeks – 7day window) follow-up with the exception of those with planned truncated follow-up.

In the first approach, regardless of whether missingness is assumed to be random or non-random, we will perform the outlined statistical procedures. Additionally, we will provide descriptive characteristics of the missing group compared to the non-missing group, exploring potential similarities or dissimilarities between them. This comprehensive approach allows for a thorough examination of the impact of missing data on our study outcomes.

In the second approach, we are aware that throughout the trial, some participants may leave the study due to a high number of exacerbations or death before reaching their 48-week follow-up. This leads to missing data that is not at random, rendering

standard imputation methods inappropriate. Therefore, the data for key secondary outcomes for these participants will be analysed in the following way:

Pattern Mixture Model:

Robustness of the results will be assessed within the pattern mixture model. A pattern mixture model is a type of statistical model used to analyse data with missing values, especially when the missingness is not at random (MNAR).

This method is a 2-stage procedure where the 1st stage involves the use of multiple imputation to impute all missing values assuming data are “missing at random”.

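### The longitudinal model adjusts for an observed baseline with no rule for a missing one, so follow-up sputum eosinophil data are discarded whenever the baseline sample was not produced

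*SAP*

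**What the plan says.** - **Model.** SAP 6.5.1.2 fits treatment arm, the stratification variables, "visit number in weeks (categorical) and baseline value as fixed effects with participant identification as a random effect". It applies to every continuous longitudinal outcome. SAP 3.2.1 defines sputum eosinophil percentage as one of these.
- **Missing data in that model.** The SAP states: "This method will be able to handle missing data during the follow-up measurements". It says nothing about a missing baseline.
- **Analysis set.** SAP 6.5.1: "All secondary outcome (except for AEs and SAEs) will be analysed on the modified intention to treat population". SAP 4.3 defines that set by availability of data: "participants with missing outcome data will be excluded from the analysis (i.e complete case analysis"), followed by "No imputation will be carried out for the missing data".
- **Imputation.** The sensitivity analysis in SAP 6.5.3 names "number of readmissions, number of exacerbations, and SGRQ (assessed for three sub-domains and the total score"). Sputum eosinophils are not on the list.
- **Sputum collection.** The footnote under Protocol 7.7.5 says that "only spontaneous sputum samples are collected as part of the standard of care". Protocol 13.5 adds: "The trial team will not be required to report protocol deviations in instances where a participant is unable to produce a sample".
- **Timing.** Under Protocol 7.6, baseline measures follow consent and randomisation and precede the first dose.
- **Fallback.** If a log transformation does not cure non-normality, SAP 5 and 6.5.1.2 allow a Mann-Whitney test without baseline adjustment.

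**The concern.** A mixed model tolerates gaps in the outcome but not in a covariate. A participant who could not produce sputum at week 0 but did so at five later visits contributes nothing to the planned comparison. Here a missing baseline is a foreseeable result of how sputum is collected.

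What is at stake is precision on an inflammatory marker listed as a secondary outcome: values already collected would go unused. The same mechanism applies to SPPB, handgrip and the continuous questionnaires, but little is lost if few of their baselines are missing.

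**Working it through.** **1. Plan's own figure.** The documents give no sample size, SD, yield or correlation for sputum eosinophils. The only stated size is for the primary outcome, and it is used here just to supply N.
- Freedman events: (1 + 0.6)² / (1 − 0.6)² × (1.96 + 0.84)² ≈ 126.
- Event probabilities: 0.65 and 1 − 0.35^0.6 = 0.467, mean 0.559.
- N = 126 / 0.559 = 225.5, rounded up to 226. Then 226 / 0.95 = 237.9, giving 238. The stated 226 and 238 reproduce.

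**2. Assumed inputs.** N = 238; six follow-up visits (weeks 4, 8, 12, 24, 36, 48); sputum yield per visit 30, 50 or 70%; within-participant correlation of the outcome (ICC) 0.3 to 0.7; weak (0.2) or strong (0.8) within-participant correlation in producing sputum.

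**3. Comparison.** Simulated random-intercept REML models, 600 data sets per scenario. 'Dropped' is the SAP model. 'Retained' fills the baseline covariate with the mean and adds a missing-baseline indicator. Results at ICC 0.6 with no treatment effect (SE in SD units):

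| Yield | Clustering | Participants used, dropped → retained | Mean SE, dropped → retained | SE ratio |
|---|---|---|---|---|
| 70% | weak | 166 → 236 | 0.091 → 0.087 | 0.96 |
| 70% | strong | 165 → 209 | 0.089 → 0.088 | 0.99 |
| 50% | weak | 115 → 225 | 0.116 → 0.100 | 0.86 |
| 50% | strong | 116 → 173 | 0.108 → 0.104 | 0.96 |
| 30% | weak | 63 → 190 | 0.171 → 0.122 | 0.71 |
| 30% | strong | 67 → 123 | 0.147 → 0.133 | 0.90 |

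At 50% yield with strong clustering, 238 − 173 = 65 participants stay out under either method because they have no follow-up sputum.

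**4. Range.** A separate set of simulations over yields of 30–70% and ICC 0.3–0.7 gave SE ratios of 0.72 to 0.98, a cut of 2–28%. The spread depends on the clustering assumed.
- In the 600-replicate grid (ICC 0.3 or 0.6), the largest variance reduction was 62%, an SE cut of 1 − √0.38 = 38%. The smallest was about 2% of variance, an SE cut of about 1%.
- A further run found no gain (ratio 1.00) at ICC 0.7 and 70% yield. My own check there gave an SE no smaller and if anything marginally larger, because one intercept variance is then fitted to participants with and without an observed baseline.
- At ICC 0.5, with 90% and 95% of baselines available, the ratios were 0.98 and 0.99.

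**5. Validity.** In the 600-replicate grid the treatment effect showed no bias. Rejection under the null was 0.037–0.070 retained and 0.045–0.065 dropped, with Monte Carlo error about 0.009.

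These runs give every participant six visits. Truncated follow-up (Protocol 4.1) and deaths would reduce the information under both methods.

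**The case against.** **The Mann-Whitney fallback needs no baseline.** This stands. Sputum eosinophils are a percentage recorded to one decimal place, and a recorded 0.0 has no logarithm, so the fallback is a real prospect. A reader might infer that everyone without a baseline sample is lost whatever happens. The documents do not support that: the loss arises only under the mixed model, raw or log scale. That model is still the planned first analysis and the only one giving an adjusted estimate.

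**The exclusion may be what the modified ITT intends.** A reader might infer that dropping these participants breaches the SAP's own analysis set. SAP 4.3 does not support that, since it specifies complete case analysis without imputation and week 0 is a listed timepoint of the outcome. The same text means that a sentence added to 6.5.1.2 alone would conflict with 4.3.

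**The remedy is not free or universal.** This also stands. It needs baseline missingness to be unrelated to arm. That is plausible because the sample is taken before dosing and with participants and investigators blinded, but it is taken after randomisation. It does not restore the precision of an observed baseline. It does not fit the ordinal eMRC score (SAP 6.5.1.4), where a mean baseline is undefined without further coding. The by-visit model in 6.5.1.2 has baseline as both outcome and covariate, so it needs its own clause.

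**The size rests on assumptions.** True. Protocol 10.8 and SAP 6.5.3 also allow additional sensitivity analyses if missingness patterns warrant them, but neither names a rule for a missing baseline.

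**Conclusion.** The point holds for continuous outcomes analysed by the mixed model. As written, a missing baseline removes all of that participant's observed follow-up values, and no section says otherwise. It matters mainly for sputum eosinophils.

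Under assumed yields of 30–70% and ICC 0.3–0.7, retaining these participants cuts the SE by roughly 2–28%. More is possible if yield is low and sputum production varies from visit to visit. Almost nothing is gained at high yield and high ICC, or where few baselines are missing. The real yield and ICC are not in the documents.

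The primary outcome is untouched: its Cox model uses no baseline sputum value. This is a cheap improvement to secondary analyses.

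**What to change.** 1. **SAP 6.5.1.2**, for continuous outcomes in the mixed model, add: *Participants with a missing baseline and at least one follow-up value are retained: the missing baseline covariate is set to the both-arm mean on the analysis scale and a missing-baseline indicator is added as a fixed effect.* A constrained longitudinal model, with baseline as an outcome and a common mean across arms, is an acceptable alternative.
2. **SAP 4.3**: add a clause that the no-imputation rule refers to outcome values, not to the baseline covariate.
3. **By-visit model in 6.5.1.2**: state that a filled-in baseline enters only as a covariate, never as an outcome.
4. **Reporting**: tabulate by arm the numbers with baseline sputum, with follow-up sputum, and with both. This also lets readers judge whether baseline missingness differs by arm.

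The cost is a few sentences, one extra covariate and one small table. No new data are needed. The rule should be fixed before database lock and before sputum results are seen by arm.
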